5 STUDY EVALUATIONS AND MEASUREMENTS

5.1 Focus Group Evaluation

Notes and transcripts from the focus groups will be read and analyzed by two different investigators. Common themes will be extracted and appropriate changes made to text message content and delivery.

5.2 Screening and Monitoring Evaluations and Measurements

5.2.1 Medical Record Review

- Weight
- Height
- BMI
- Most recent HbA1c value
- Current diabetes treatment plan
- Number of DKA admissions

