3.2.1 Screening Phase

Potential subjects will be recruited from the CHOP Endocrinology and Diabetes outpatient clinic. Clinic schedules will be reviewed for determination of potential subjects as per the inclusion criteria above. Some subjects will be pre-screened for interest only, without eliciting PHHI, by telephone prior to their clinic visit. Subjects will be approached during their clinic visit and informed about the current study. If the subject agrees to participate, informed consent (from caregiver if subject is < 18 y/o and from subject if he/she is >18 y/o) as well as assent if subject is < 18 y/o will be obtained. HbA1c and diabetes treatment plan will be collected from the medical record.

3.2.2 Phase 1

This phase will start enrollment. Subjects will be registered into the MyDiaText website by research staff. At registration, MyDiaText will randomize half of the subjects to the intervention group and the other half to the control group. At this time, SCI will be administered via a text message link to the MyDiaText website; this will serve also to ensure the phone number for the patient was entered correctly and that account is active for log-in. All subjects will get \$5 upon completion of baseline self-care inventory. All subjects, control and intervention, will create a profile in the MyDiaText system. This profile will consist of his/her name, birthday, gender, ethnicity, phone number, and email. All subjects will be following their diabetes care plan as dictated by their primary diabetes provider. The subjects in the intervention group will start receiving the text messaging intervention as described in the intervention section (section 7). Subjects in the intervention group will be instructed to respond to each text as a proxy for having read it. Previously, a point system reflected scoring on quizzes and educational activities. To update the text messages based on current technology, all quizzes have been transitioned into text messages. To address gaps in research, a specific reward paradigm was created based on the concept of “streaks,” or reward for consecutive days of engagement in the application. Those with the longest “streak” will be placed in a drawing for an extra cash prize of \$10 every two weeks.

3.2.3 Phase 2

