3.5 Study Population

3.5.1 Inclusion Criteria

- 1) Males or females age 12 to 18 years.
- 2) Have a diagnosis of T1DM for more than 1 year.
- 3) HbA1c \geq 8% but $<$ 14%.
- 4) Have been in seen in the diabetes clinic in the last 6 months.
- 5) Own a personal mobile device with unlimited text messaging plan.
- 6) Parental/guardian permission (informed consent) and, if appropriate, child assent.

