5.3 Efficacy Evaluations

5.3.1 Diagnostic Tests, Scales, Measures, etc.

The efficacy of this intervention in improving glycemic control will be determined using HbA1c values. HbA1c is checked every 3 months as part of the diabetes treatment plan. These values will be collected as a research lab at each visit.

The efficacy of this intervention in improving diabetes self-management skills will be determined by the SCI questionnaire. This will be completed at each study visit.

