6.3.2 Efficacy Analysis

The primary analysis will include all subjects randomized at Visit 1 who have gotten HbA1c measurements at visit 2. The primary efficacy endpoint will be the change in SCI Score.

The first analysis will be change in SCI score from visit 1 to visit 2 comparing treatment and control groups. For this analysis we will use paired t-tests to test the null hypothesis of no difference in change in SCI scores at the two-sided $\alpha = 0.05$ level.

The secondary analysis will be the change in HbA1c between the intervention and control group from visit 1 to visit 2. For this analysis we will use two sample t-test to test the null hypothesis of no difference in the change in HbA1c at the two-sided $\alpha = 0.05$ level.

An additional secondary analysis will be the durability of the text messaging intervention from visit 2 to 3. SCI score and HbA1C will continue to be tracked to compare visit 1 to visit 3 and visit 2 to visit 3 at study conclusions.

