6.4 Sample Size and Power

The average HbA1c in adolescents at the CHOP Endocrinology and Diabetes clinic is 9.11% with a SD of 2.26%. Given this average HbA1c and its SD, a sample size of 164 subjects would be needed to observe a difference of 1% in mean HbA1c between groups at a

0.05 level of significance with 80% power in a cross-over study. We will aim to recruit up to 200 subjects out of over 1400 adolescents with T1DM seen at the CHOP Diabetes clinics for their routine care on a yearly basis.

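### The HbA1c comparison uses neither Visit 1 HbA1c as a covariate nor the earlier routine values probably in the same chart: a cheap gain in precision to consider, not a flaw in validity

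*Combined protocol and SAP*

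**What the plan says.** Protocol section 5.2.1 lists the items taken at chart review. For HbA1c there is one: "Most recent HbA1c value". Section 3.2.1 says of screening that "HbA1c and diabetes treatment plan will be collected from the medical record", and sections 3.2.3 and 3.2.4 repeat this for the later visits. None of them asks for an earlier series.

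Three statements bear on whether earlier values exist. Section 5.3.1 says "HbA1c is checked every 3 months as part of the diabetes treatment plan". Section 3.5.1 requires that subjects "Have a diagnosis of T1DM for more than 1 year" and "Have been in seen in the diabetes clinic in the last 6 months".

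The HbA1c analysis is in section 6.3.2: "For this analysis we will use two sample t-test to test the null hypothesis of no difference in the change in HbA1c", from Visit 1 to Visit 2, two-sided at 0.05. No covariate is named there or elsewhere.

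Section 6.4 gives the only sample-size figures: "The average HbA1c in adolescents at the CHOP Endocrinology and Diabetes clinic is 9.11% with a SD of 2.26"%, and "a sample size of 164 subjects would be needed to observe a difference of 1% in mean HbA1c between groups", with 80% power at the 0.05 level. Recruitment stops at 200 (section 3.4.2), allocated half and half (section 3.3).

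**The concern.** A single HbA1c is a noisy reading of a subject's usual level. A change score subtracts that reading in full, whatever its correlation with the outcome, and so carries more noise than a model that estimates the weight. Values from the preceding year, where they exist, describe the usual level better than one reading can. Being dated before randomisation, they cannot be affected by arm, so using them as a covariate does not bias the comparison.

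What is at stake is the width of the HbA1c confidence interval. HbA1c is the only outcome with a sample-size calculation. The planned difference of 1 point is what section 1.1 gives as the upper end of reported improvements, and section 1.3 describes messaging trials with little or no significant HbA1c change, so precision for effects below 1 point is of interest. Timing also matters: Visit 1 adjustment can be added from data already planned, but values never abstracted cannot be used later.

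**Working it through.** **Inputs from the documents.** Mean 9.11, SD 2.26, difference 1 point, 80% power, two-sided 0.05 (sections 6.4 and 6.3.2); entry HbA1c from 8 to below 14 (section 3.5.1); 200 subjects, 1:1.

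**Assumptions.** The correlation r between visits is not given; I use 0.5 to 0.8. HbA1c is taken as normal before the entry restriction. All 200 are analysed, 100 per arm, unless stated.

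**1. The plan's own figure.** n per arm = 2 × 2.26² × (1.96 + 0.84)² / 1² ≈ 80.2, so 81 per arm and 162 in total; the t-based version gives 82 per arm, 164 in total. The stated 164 reproduces as a two-group comparison of single values, although section 6.4 calls the study a cross-over. With 100 per arm and SD 2.26, power for 1 point is about 88%.

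**2. Change score against Visit 1 adjustment.** A normal with mean 9.11 and SD 2.26, truncated to 8–14, has SD 1.428. Then:
- change-score variance = 2.26²(1 − r²) + (1 − r)² × 1.428²
- residual variance adjusting for Visit 1 = 2.26²(1 − r²)

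| r | SD, change | SD, Visit 1 adjusted | variance cut |
|---|---|---|---|
| 0.5 | 2.08 | 1.96 | 12% |
| 0.6 | 1.90 | 1.81 | 9% |
| 0.7 | 1.67 | 1.61 | 7% |
| 0.8 | 1.39 | 1.36 | 4% |

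**3. Adding k earlier values, equal correlation.** With k earlier values plus Visit 1, residual variance = 2.26² × [1 − (k+1)r² / (1 + kr)]. At r = 0.7 the SDs are 1.47, 1.41 and 1.37 for k = 1, 2, 3. The cut beyond Visit 1 adjustment, over r = 0.5 to 0.8, is 11–20% for k = 1, 17–27% for k = 2 and 20–31% for k = 3. The entry restriction does not change these percentages, because it acts on Visit 1, which is already in the model.

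**4. Other correlation structures.**
- Stable part plus decay, correlation 0.4 + 0.5 × 0.6^lag or 0.5 + 0.35 × 0.6^lag: a further cut of 4.1% to 8.9% for k = 2 to 3.
- A mix with half of r stable, 5% noise and the rest decaying: 2.3% to 3.2% for k = 2 to 3 (1.4% to 2.0% for k = 1).
- Pure first-order autoregressive: 0%.

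**5. What this does to the comparison, at r = 0.7 and 100 per arm.** The 95% half-width is 1.97 × SD × √(2/100).

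| Analysis | SD | half-width | power, 1 point | power, 0.5 point | detectable at 80% |
|---|---|---|---|---|---|
| Change score (planned) | 1.67 | 0.47 | 98.8% | 56% | 0.67 |
| Visit 1 adjusted | 1.61 | 0.45 | 99.2% | 59% | 0.64 |
| + 1 earlier, equal correlation | 1.47 | 0.41 | above 99% | 67% | 0.59 |
| + 2 earlier, equal correlation | 1.41 | 0.39 | 99.9% | 71% | 0.56 |
| + 3 earlier, equal correlation | 1.37 | 0.38 | 99.9% | 73% | 0.55 |

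Under decay, cutting the Visit 1-adjusted variance by 4.1% to 8.9% moves power at 0.5 point from 59% to about 60–63%. Under the autoregressive case it stays at 59%. With 82 per arm analysed, the planned test still has 96.8% power for 1 point. The 0.5-point difference is illustrative; the plan does not target it.

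**The case against.** The strongest case against is that nothing here is wrong. A t-test on change from a randomised baseline is valid and unbiased, one baseline value is ordinary practice, and at the planned difference power is about 99% at r = 0.7. All of that stands. A reader might infer that the HbA1c test is biased or that the trial is underpowered for its stated target; the documents support neither.

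A reader might also take a variance cut of 24% to 28% (equal correlation 0.7, two or three earlier values) as the size of the loss. That requires a value from many months back to predict Visit 2 as well as the Visit 1 value does. The documents give neither a correlation nor a structure, and plausible alternatives give far less, down to zero.

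Nor do the documents show that every chart holds several earlier values. Eligibility guarantees only one clinic visit in the last 6 months, and a 3-monthly schedule in the treatment plan is not a record of attendance. Section 5.3.1 also describes trial HbA1c as a research lab, while sections 3.2.1 to 3.2.4 take it from the medical record; if the methods differ, earlier chart values may correlate less.

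Finally, section 6 makes the Self-Care Inventory score primary and HbA1c secondary, and that score has no comparable chart history. This limits the weight of the point. What survives is that both additions are unbiased and cheap, and that the first needs no new data.

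**Conclusion.** Worth considering; the loss is precision, not validity. Visit 1 adjustment comes first, with a variance reduction of about 4% to 12% against the change score for correlations of 0.5 to 0.8 and entry truncation applied to Visit 1. Earlier values may add a further reduction of 0% to about 31%: about 11–31% under equal correlation with one to three values per subject, about 2–9% under decay around a stable level, 0% under a pure autoregressive series. These are results of assumptions, not of the documents, and they suppose every subject has the stated number of values.

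In practice the gain is a narrower interval and power for effects smaller than planned: at 0.5 point and r = 0.7, 56% for the planned test, 59% adjusting for Visit 1, and 59–73% with earlier values depending on structure. How much this matters depends on reconciling HbA1c's status between the abstract, synopsis and section 2 on one side and section 6 on the other.

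**What to change.** 1. In section 6.3.2, compare arms on HbA1c with a linear model containing arm and Visit 1 HbA1c, in place of the t-test on change.
2. In section 5.2.1, at Visit 1, abstract the Visit 1 HbA1c and also all HbA1c values with dates in the 12 months before it. In section 6.3.2, add the mean of those earlier values as a pre-specified second covariate, using only values dated before randomisation. For subjects with none, use the overall covariate mean plus a missing indicator, so that nobody is dropped for lack of history.
3. State which status HbA1c has, and whether trial HbA1c is a research lab or a chart value.

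Step 1 costs one line of text. Step 2 costs a few fields at a chart review already planned, and one or two model degrees of freedom; some subjects will contribute few or no earlier values. No extra visit, blood draw or subject is needed. Step 2 should be specified before abstraction begins, and both covariates before outcomes are seen.

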5.2.2 Laboratory Evaluations

- Hemoglobin A1c

5.2.3 Other Evaluations, Measures

- Self-Care Inventory

5.3 Efficacy Evaluations

5.3.1 Diagnostic Tests, Scales, Measures, etc.

The efficacy of this intervention in improving glycemic control will be determined using HbA1c values. HbA1c is checked every 3 months as part of the diabetes treatment plan. These values will be collected as a research lab at each visit.

The efficacy of this intervention in improving diabetes self-management skills will be determined by the SCI questionnaire. This will be completed at each study visit.

5.4 Safety Evaluation

Given the nature of the intervention, no adverse events that will require intervention or monitoring will occur.

6 STATISTICAL CONSIDERATIONS

6.1 Primary Endpoint

The primary endpoint will be the change in SCI score between Visit 1 and Visit 2 in control group as compared to intervention group

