6.3.2	Efficacy Analysis	10
6.4	SAMPLE SIZE AND POWER	10
7	STUDY INTERVENTION	12
7.1	DESCRIPTION	12
7.1.1	Treatment Compliance and Adherence	12
8	SAFETY MANAGEMENT	13
8.1	CLINICAL ADVERSE EVENTS	13
8.2	ADVERSE EVENT REPORTING	13
9	STUDY ADMINISTRATION	14
9.1	TREATMENT ASSIGNMENT METHODS	14
9.1.1	Randomization	14
9.1.2	Blinding	14
9.1.3	Unblinding	14
9.2	DATA COLLECTION AND MANAGEMENT	14
9.3	CONFIDENTIALITY	14
9.4	REGULATORY AND ETHICAL CONSIDERATIONS	15
9.4.1	Data and Safety Monitoring Plan	15
9.4.2	Risk Assessment	15
9.4.3	Potential Benefits of Trial Participation	15
9.4.4	Risk-Benefit Assessment	15
9.5	RECRUITMENT STRATEGY	15
9.6	INFORMED CONSENT/ASSENT AND HIPAA AUTHORIZATION	16
9.6.1	Focus Group	16
9.6.2	Intervention	16
9.7	PAYMENT TO SUBJECTS/FAMILIES	16
9.7.1	Payments to subject for time, effort and inconvenience (i.e. compensation)	16
10	PUBLICATION	15
11	REFERENCES	17

ABBREVIATIONS AND DEFINITIONS OF TERMS

CHOP	Children’s Hospital of Philadelphia
T1DM	Type 1 diabetes mellitus
HbA1c	Hemoglobin A1c
SCI	Self-Care Inventory

ABSTRACT

Context:

Type 1 diabetes mellitus is one of the most common chronic diseases in childhood in the United States and its incidence continues to rise. Glycemic control during adolescence can be extremely difficult to achieve due to various biological, social, behavioral, and psychological factors. Development of effective and sustainable interventions to improve diabetes control and diabetes self-management during adolescence is of utmost importance to prevent short- and long-term complications and improve the quality of life of adolescents with type 1 diabetes mellitus.

Objectives:

The primary objective of this study is to test a text messaging intervention using MyDiaText and to determine whether such an intervention will decrease HbA1c in children 12 to 18 years with type I diabetes mellitus.

The secondary objectives is to determine if a text messaging intervention using MyDiaText will improve diabetes self-management skills as measured by the Self-Care Inventory (SCI) in children 12 to 18 years.

Study Design:

Randomized trial

Setting/Subjects:

This study will take place at the Children's Hospital of Philadelphia.

It will include 200 adolescents aged 12-18 with T1DM.

Study Interventions and Measures:

This study will use MyDiaText text messaging program as an intervention.

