The main outcome measure will be change HbA1c. The secondary outcome measure will be change in scores of the Self-Care Inventory questionnaire.

PROTOCOL SYNOPSIS

[figure not shown]
Study Title	MyDiaText: Texting the Way to Better Diabetes Control
Funder	NIH T32 Grant-Pediatric Endocrinology Division of CHOP
Clinical Phase	intervention
Study Rationale	Optimal control of type 1 diabetes may prevent, or at least decrease the risk of, diabetes complications. Adolescents with diabetes often have difficulty adhering to a diabetes management plan such a monitoring of blood glucose levels, administering insulin, and eating healthy. There is a need for an intervention that will resonate with youth and support adolescents with type 1 diabetes to improve their self-management practices in order to improve their glycemic control and prevent or reduce the risk of short- and long-term complications.
Study Objective(s)	
Primary
 
 To develop a text messaging intervention using MyDiaText and to determine whether such an intervention will decrease HbA1c in children 12 to 18 years 
Secondary
 
 To determine if a text messaging intervention using MyDiaText will improve diabetes self-management skills as measured by the Self-Care Inventory (SCI) in children 12 to 18 years
Test Article(s)	The intervention will consist of daily text messages sent to the subject's personal mobile device. Previously developed text messages and quiz questions based on the ADA behavior goals will be used for this intervention.
Study Design	Randomized trial
Subject Population key criteria for Inclusion and Exclusion:	
Inclusion Criteria
 
 Subjects age 12 to 18 year of age. Have a diagnosis of T1DM for more than 1 year. HbA1c \geq 8% but $<$ 14%. Have been seen in the diabetes clinic in the last 6 months. Own a personal mobile device with unlimited text messaging plan. Parental/guardian permission (informed consent) and, if appropriate, child assent. 
Exclusion Criteria
 
 Non-English speaking. Significant cognitive disability or major organ illness. Hemolytic anemia.

4. Ongoing oral steroid use	
Number Of Subjects	200 subjects will be recruited from Diabetes Clinics affiliated with the Children’s Hospital of Philadelphia
Study Duration	Each subject’s participation will last for approximately 180 days

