Study Phases	(1) Pre-screening : focus groups to determine details of the intervention
Screening	(2) Screening : screening for eligibility and obtaining consent, review medical record for HbA1C, obtain baseline Self-Care Inventory score
Study Treatment	(3) Intervention : review medical record for HbA1C, obtain Self-Care Inventory score
Follow-Up	(4) Follow-up : review medical record for HbA1C, obtain Self-Care Inventory score, complete satisfaction survey
Efficacy Evaluations	The primary efficacy endpoint will have two parts: the change in HbA1c between control and intervention groups between visit 1, 2 and 3.
Safety Evaluations	Adverse events are not anticipated in this study.
Statistical And Analytic Plan	Descriptive data analysis will include estimating means and standard deviations for continuous variables and counts and proportions of categorical variables for all aims. Two sample t-tests will be used to evaluate changes in HbA1c and SCI scores between the control and intervention groups and paired t-tests (or nonparametric methods if data is not normally distributed) will be used to compares the above changes within each group.
Data and Safety Monitoring Plan	The PI will monitor study progress, ensure the accuracy and security of the data, and ensure subject safety.

TABLE 1: SCHEDULE OF STUDY PROCEDURES

Study Phase	Screening	Control	Intervention	Follow-Up
Visit Number		1	2	3
Study Days		90 (+/- 30 days)	90 (+/- 30 days)	1
Informed Consent/Assent	X			
Review Inclusion/Exclusion Criteria	X			
Randomization	X			
Intake Questionnaire		X		
Height and Weight		X	X	X
HbA1c		X	X	X
SCI Questionnaire		X	X	X
Exit Questionnaire (Subjective Assessment of Intervention)				X

FIGURE 1: STUDY DIAGRAM

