2.1 Primary Objective (or Aim)

The primary objective of this study is to develop a text messaging intervention using MyDiaText and to determine whether such an intervention will decrease HbA1c in children 12 to 18 years. This will be divided into 2 parts:

- To determine whether this intervention will decrease HbA1c in children 12 to 18 years after 3 months +/- 1 month.
- To determine whether the effect of the intervention persists after an additional 3 months +/- 1 month of intervention.

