2.2 Secondary Objectives (or Aim)

The secondary objectives are to:

- Determine if a text messaging intervention using MyDiaText will improve diabetes self-management skills as measured by the Self-Care Inventory (SCI) in children 12 to 18 years.
- Analyze the response rate to educational text messages when a reward paradigm, in which children are intermittently rewarded for engaging in the application for multiple days in a row, is administered.

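### The plan names two different primary endpoints: SCI change in section 6, HbA1c change in the abstract, synopsis and objectives, with nothing to say which governs

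*Combined protocol and SAP*

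**What the plan says.** **HbA1c primary, SCI secondary.** The abstract gives the aim as "primary objective of this study is to test a text messaging intervention using MyDiaText and to determine whether such an intervention will decrease HbA1c" and then ranks the outcomes: "The main outcome measure will be change HbA1c. The secondary outcome measure will be change in scores of the Self-Care Inventory questionnaire". The synopsis, under Efficacy Evaluations, says "The primary efficacy endpoint will have two parts: the change in HbA1c between control and intervention groups between visit 1, 2 and 3". Section 2.1 splits the primary objective into two parts, "To determine whether this intervention will decrease HbA1c in children 12 to 18 years after 3 months +/- 1 month" and "To determine whether the effect of the intervention persists after an additional 3 months +/- 1 month of intervention". Section 2.2 places SCI among the secondary objectives.

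**SCI primary, HbA1c secondary.** Section 6.1 says "The primary endpoint will be the change in SCI score between Visit 1 and Visit 2 in control group as compared to intervention group". Section 6.2 lists HbA1c change as a secondary endpoint. Section 6.3.2 names SCI change as the primary efficacy endpoint, makes the HbA1c comparison from Visit 1 to Visit 2 the secondary analysis, and treats results to Visit 3 as an additional secondary analysis.

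**Related statements.** Section 6.3.2 restricts the primary analysis to randomized subjects with an HbA1c at Visit 2. It specifies paired t-tests for the between-arm SCI comparison, whereas the synopsis says "Two sample t-tests will be used to evaluate changes in HbA1c and SCI scores between the control and intervention groups" and keeps paired tests for change within a group. Section 6.4 sizes the trial on HbA1c alone and describes the design as cross-over, although section 3.3 randomizes half the subjects to each of two arms.

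**The concern.** A reader cannot tell whether the trial succeeds on HbA1c or on SCI. If the two outcomes disagree, the plan supports either as the main result. The trial is unblinded (sections 3.3 and 9.1.2), and one of the two candidates is a self-care questionnaire, so which outcome counts matters to the interpretation.

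Each reading leaves a defect:

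- **If section 6 governs,** the primary test has no stated effect, SD or power. Its analysis set depends on a different outcome, and the declared primary objective is reduced to a secondary test.
- **If the objectives govern,** section 6 names the wrong endpoint. It also moves the Visit 3 part of the primary objective to secondary without acknowledging that this departs from section 2.1.

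**Working it through.** **1. The statements side by side**

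| Item | Abstract, synopsis, 2.1-2.2 | Sections 6.1-6.3.2 |
|---|---|---|
| Primary outcome | HbA1c change | SCI change |
| Secondary outcome | SCI change | HbA1c change |
| Primary period | To Visit 2, and persistence to Visit 3 (2.1, synopsis) | Visit 1 to Visit 2 |
| Visit 3 | Part of the primary | Secondary |
| Between-arm test for SCI | Two-sample t | Paired t |

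This is more than a difference between objective and endpoint wording: the synopsis and 6.3.2 both use the term primary efficacy endpoint, for different outcomes.

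**2. Analysis set.** Under sections 3.2.3 and 5.3.1, HbA1c is measured at the clinic visit, while the second SCI is requested by text message with at most two reminders. Under 6.3.2 a subject with a Visit 2 SCI but no HbA1c is left out of an SCI analysis. A subject with HbA1c but no SCI is counted in with no outcome.

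**3. The plan's own sample size.** Inputs: difference 1%, SD 2.26%, alpha 0.05 and power 80% (6.4); two-sided (6.3.2; 6.4 is silent); 1:1 allocation (3.3).

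- Standardized effect: 1/2.26 = 0.442.
- Normal approximation: n per arm = 2 × (1.960 + 0.842)² × 2.26² / 1² = 80.2, so 81 per arm, 162 in total.
- Two-sample t-test: 81.15, so 82 per arm, 164 in total. This matches the stated figure; power is 80.4%.
- A paired or cross-over calculation with SD of differences 2.26% needs about 43 in total, and a one-sided parallel test 128. Neither matches.

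The 164 is therefore a parallel-group HbA1c figure, despite the cross-over label.

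**4. HbA1c power with 200 recruited** (t-test, SD 2.26%; the dropout rates are assumptions, as the plan gives none):

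| Analysed per arm | Loss | Power |
|---|---|---|
| 100 | 0% | 87.6% |
| 90 | 10% | 83.9% |
| 82 | 18% | 80.4% |
| 80 | 20% | 79.4% |

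Section 6.4 gives the SD of HbA1c in the clinic, not the SD of change, and names no visit. If 2.26% applies at both visits, SD of change = 2.26 × √(2(1 − ρ)). At assumed correlations ρ of 0.3, 0.5 and 0.7 this is 2.67, 2.26 and 1.75, and 100 per arm give 74.9%, 87.6% and 98.0% power.

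**5. SCI.** No effect or SD is given, so no required sample size can be computed. In units of the SD of the SCI change score, the difference detectable at 80% power is 0.398 with 100 per arm, 0.420 with 90 and 0.446 with 80. With 200 analysed, power at assumed effects of 0.2, 0.3, 0.4 and 0.5 SD is about 29%, 56%, 80% and 94%.

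**6. Error rate, for illustration only.** If either outcome at one visit could be called primary after the results are seen, the chance of at least one false positive is 1 − 0.95² = 9.75% for independent tests. At assumed correlations of 0.3, 0.5 and 0.7 between the test statistics it is 9.5%, 9.1% and 8.3%. Section 6.3.2 read alone keeps its primary test at 5%.

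**The case against.** The best defence is that sections 6.1, 6.2 and 6.3.2 all rank SCI first, which is compatible with a deliberate change that was not carried into the front matter. That may be so. But the current text does not say it, and section 6 still sizes the trial on HbA1c and selects its analysis set by HbA1c. It cannot simply be taken as governing, and the sponsor has to state what was intended.

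Several narrower points deserve weight:

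- **Visit 3.** Section 6 does openly label the Visit 3 analyses as secondary. What is missing is any acknowledgement that this departs from section 2.1.
- **The 18% loss limit.** It holds only if the SD of the analysed variable is 2.26%. It is not a general threshold.
- **The 74.9% figure.** It ignores the entry range of HbA1c from 8% to below 14%. If clinic values are assumed bivariate normal (mean 9.11%, SD 2.26%) and baseline is truncated to that range, baseline SD is about 1.43%. SD of change is then √((1 − ρ)² × 1.43² + (1 − ρ²) × 2.26²), or about 2.38, 2.08 and 1.67 at ρ of 0.3, 0.5 and 0.7. Power with 100 per arm becomes about 84%, 92% and 99%. This too rests on assumptions, but it shows that HbA1c power may be better than the simpler formula suggests.
- **SCI losses.** They may differ from HbA1c losses because the two are collected differently, so the 10-20% range is only illustrative for SCI.
- **The error rate.** No passage permits choosing the primary after the fact, so the inflated rate is not a property of the plan.
- **The paired test and the cross-over label.** Both would need correction whichever endpoint governs. They do not prove the main conflict.

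None of these removes the contradiction over which outcome is primary.

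**Conclusion.** The concern holds, with high confidence, and must be fixed: the plan contains two incompatible primary endpoints and no rule for choosing between them. That conclusion comes from the text and depends on no assumed figure.

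The consequence differs by endpoint. For HbA1c, the planned 200 subjects are adequate for a 1% difference if 2.26% is the SD of the analysed variable and loss is no more than 18%; the answer shifts with the unstated SD of change. For SCI, adequacy is unknown unless the target is about 0.40 SD of change or larger (0.42-0.45 SD with an assumed 10-20% loss). The severity does not rest on the illustrative error rate.

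**What to change.** Before outcome data are examined, name one primary endpoint and one time point and use them in every section.

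**If HbA1c is primary** (closest to the stated objectives and the only outcome with a power basis): rewrite 6.1, 6.2, 6.3.2 and the synopsis to agree. If Visit 1 to Visit 2 is the primary period, state that the Visit 3 persistence part of 2.1 and the synopsis becomes secondary. This is a wording amendment with no added procedures. The 80% power is kept under the SD and loss conditions given above; stating the SD of change that is assumed would settle the first of these.

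**If SCI is primary:** change the abstract, synopsis and 2.1-2.2, and relabel the HbA1c power statement as secondary. Define the 6.3.2 analysis set by SCI data. State the SCI precision with 200 subjects, with a reason why a difference of that size is meaningful. The cost is the wording plus an SCI effect and SD, and the sample size may prove too small.

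**In either case:** replace the paired t-test in 6.3.2 with the synopsis's two-sample comparison of change, correct the cross-over label in 6.4, and label the remaining outcomes supportive. A fixed testing sequence is needed only if confirmatory claims on them are planned.
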